Appendix R

Pre-Intervention Questionnaire (Red Cap)

DEMOGRAPHIC INFORMATION

1. Name: _____ Study ID: _____

2. Date of Birth: _____

3. Gender: _____

4. Race/ Ethnicity (check one):

White/ Caucasian Black/ African American Asian/ Pacific Island

Hispanic/ Latino Other: _____

5. Highest level of education: _____

6. Type of dwelling/ residence: House Apartment or Condominium Other: _____

Address: _____

7. Phone number: _____

8. Email address: _____

9. Preferred form of communication: _____

PAST MEDICAL HISTORY

10. **Check those questions to which your answer is yes (leave others blank).**

Motion Sickness, Dizziness, Vertigo (moving vehicle, playing games, roller coaster rides, etc.) _____

Previous brain injuries (e.g., trauma): _____

Falls: _____

Seizures, Blackouts: _____

Claustrophobia: _____

Sensitivity to light: _____

Sensitivity to loud noises: _____

Glasses Contact Lenses Cataracts Hearing aides

STROKE HISTORY

11. Date of most recent stroke: _____

12. Description of Paralysis:

13. Description of Cognitive Impairment:

14. Prior Occupational and Cognitive Rehabilitation (when/ where, goals focused on)

13. Treating medical provider _____

14. Prior stroke history _____

Current Medications & Supplements

Hospitalization History

CAREGIVER INFORMATION

15. Relationship to the Patient: _____
16. Does the caregiver live with the participant? _____
17. Who lives in the participant's household? _____
18. Date of Birth: _____
19. Gender: _____
20. Highest level of education: _____
21. **Race/ Ethnicity (check one):**

White/ Caucasian Black/ African American Asian/ Pacific Island

Hispanic/ Latino Other: _____

PRIOR TECHNOLOGY EXPERIENCE USE OF THE STROKE SURVIVOR PARTICIPANT

22. Do you have internet access at home? Type: _____
23. How many hours a day do you use computers, tablets, or smartphones during the day?
 0-2 hrs 3-4 hrs 4-8 hrs More than 8 hrs
24. Have you ever played video games previously? If so, please describe

25. Have you ever used a virtual reality headset? If so, please describe

Appendix S
Post-Intervention Questionnaire

Stroke Survivor Participant Questions

What did you enjoy the most about using the VR headset for stroke rehabilitation?

PROBES: (1,2, 4,7, 8 from original list)

- Can you describe the Job Simulator games that you played?
- How well did these activities simulate “real-life”?
- Describe how often you might use the VR headset at home for stroke rehabilitation?

What did you enjoy the least about using the VR headset for stroke rehabilitation?

PROBES: (Q's 3, 5,6, 9 from original list)

- Can you discuss any symptoms or aspects of the VR headset that would prevent you from using the VR headset again?
 - How did it feel to use the VR headset?
 - Can you describe how the tutorial provided at the first session assisted you in understanding how the headset works? What could we do differently?

Do you have any other comments that you would like to share regarding the rehabilitation session with the VR headset?

Stroke Survivor's Perspective on Relationship

IF THE CAREGIVER STAYED REGULARLY TO OBSERVE THE SESSIONS

- How would you describe your caregiver's participation in the rehabilitation session upon your own progress?
- How do you feel that your caregiver's participation will impact your progress during home rehabilitation sessions using a VR headset?
- How do you feel about your caregiver's encouragement during your rehabilitation session?
- What type of intervention with your caregiver would you prefer during your rehabilitation sessions using a VR headset?

PROBE:

- Can you describe how your caregiver's participation in the rehabilitation sessions have /have not improved your level of connection to one other? In what ways?
- Can you describe how your caregiver's participation in home rehabilitations sessions using a VR headset may impact your level of connection to one another? In what ways?

- Is there anything else you would like to share about the quality of your relationship with your caregiver? Any ideas on how this VR technology may be used to improve the quality of your relationship?
- Do you have any other thoughts or comments about using the VR headset in a home setting?

IF THE CAREGIVER DID NOT STAY REGULARLY TO OBSERVE THE SESSIONS

- Would you have preferred for your caregiver to stay and observe your rehabilitation sessions using the VR headset?
- Do you feel that having your caregiver observe or participate during the VR sessions would have helped you feel more engaged during the sessions?
- Do you feel that having the VR headset at home would give you an opportunity to connect with your caregiver? What about other family members or friends?
- Do you have any other thoughts or comments about using the VR headset in a home setting?

Caregiver Questions

Tell me your thoughts about your stroke survivor using the VR headset for their rehabilitation sessions.

PROBE: What are your thoughts on using the VR headset for home rehabilitation?

IF THE CAREGIVER STAYED REGULARLY TO OBSERVE THE SESSIONS

1. Do you think that the stroke survivor would use the VR headset for home rehabilitation?
2. How did you feel about your involvement during the rehabilitation sessions?
3. How do you feel about being involved in stroke participant's rehabilitation sessions using a VR headset in the home environment?
4. Describe how your participation in your stroke survivor's rehabilitation sessions have /have not improved your level of connection to one other? In what ways?
5. Describe how your participation in your stroke survivor's rehabilitation sessions using the VR headset may impact your level of connection to one another? In what ways?
6. Is there anything else you would like to share about the quality of your relationship with your stroke survivor? Any ideas on how this VR technology may be used to improve the quality of your relationship?

IF THE CAREGIVER DID NOT STAY REGULARLY TO OBSERVE THE SESSIONS

1. Do you think that the stroke survivor would use the VR headset for home rehabilitation?
2. How do you feel about being involved in stroke participant's rehabilitation sessions using a VR headset in the home environment?
3. Describe how your participation in your stroke survivor's rehabilitation sessions using the VR headset may impact your level of connection to one another? In what ways?
4. Do you think that other family members and/ or friends would be interested in

participating in the home rehabilitation session using the VR headset?

- Do you think that the VR headset is a good way to emotionally connect with the stroke survivor? Why/ why not?

EXPLORING STROKE SURVIVOR TREATMENT BURDEN AND CAREGIVER STRESS

Thank you for taking the time to discuss your perspectives and experiences in caring for someone who has had a stroke.

We are also very interested in learning more about caregivers' day to day experiences in caring for their stroke survivor. From helping with activities of daily living (like dressing, bathing) to navigating medications, therapy appointments, and insurance issues – we believe that very little is known about these issues and how stroke survivors and their caregivers can be better supported.

My role here is to listen to your experiences and identify areas where CGs could be better supported. I am not here to judge or criticize anything that you share with me. However, I am obligated to inform you that Texas state law requires that I report suspicions of current mistreatment.

I want to reassure you that anything that you share with me today is completely anonymous. Although I am recording this interview to ensure that I am accurately capturing what you're saying, the data that you provide won't be shared outside of my research team. The transcripts that we produce will be de-identified. Do you have any questions?

Interview Questions	Probe
1. Tell me about your relationship with the stroke survivor that you care for.	
 How long have you known them? When did stroke occur (how long have you been caring from them since their stroke)? How have roles changed in this relationship since the person has had a stroke.
2. The level of assistance that stroke survivors require as they recover can depend on the type of stroke, and the person's level of function before the stroke. Tell me about the type of support that you've provided (e.g., physical, emotional, healthcare logistic related etc.) for your stroke survivor.	
 How prepared were you in providing this support? What helped you along the way to become more comfortable in providing this care? What was/is most challenging about this?
3. Navigating stroke care is a new experience for many people. Walk me through how the experience was for you and your loved one to: 
 Transition home from the hospital Interact with others involved in your stroke care (e.g., stroke care team, PT, OT etc.) Manage and organize treatment 
 Traveling to appointments Time off from your own work 	
 How prepared were you to deal with this? 
 What types of supports were offered? What would have helped the most at that particular time?


 - Managing care plans for other chronic conditions - Medication management 	

4. Caregiving can be a stressful and challenging journey. It's not uncommon for caregivers to feel angry, frustrated, or hopeless from time to time.
 
Can you please describe a time when you might have felt overwhelmed with your CG activities?
	
 • What was the context? • How in-control of your emotions did you feel during this time? • Did you act/behave in a way that you wouldn't normally? • Tell me about a time when you might have pushed your loved one's buttons out of frustration. • How do you think this affected your loved one and their care? • Looking back, is there anything you would have liked to do differently?

Conclude interview and thank participant for their time.

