Number of sessions attended; Duration (minutes) of session	Session 1 – Last Session		

Table 1

Potential Problems and Alternative Approaches

- If the participant cannot complete the study, then we will offer home exercises selected by the therapist from Appendix N and they will exit the study.
- Stroke survivors will be encouraged to take a brief break every 20 minutes due to potential for visual fatigue. If the participant develops simulator sickness (e.g., nausea, dizziness, etc.) or wishes to stop the session for any reason, we will immediately stop the session and allow the participant to rest until the symptoms subside.
 - If the participant's symptoms do not resolve immediately, then we will take the patient's blood pressure, pulse, and/ or temperature as appropriate.
 - We will call 911 should the participant require immediate assistance. If the participant does not require immediate care, we will encourage the participant to be evaluated at an urgent care and/ or their doctor's office.

- All adverse events will be monitored, documented, and reported to the ethics committees. Progress addressing adverse events will be recorded until their resolution.

Data Management

- We will record the Oculus gaming sessions using the camera located in the living room for the therapists to review after the session to evaluate the participants' progress.
- Informed consent documents and de-identified, demographic and participant satisfaction surveys will be stored electronically via REDCap,™ following UTHealth security procedures. Qualitative interview data will be digitally recorded; these raw audio files will be stored in a secure folder of the PI's UTHealth, OneDrive. Transcribed, de-identified interview data will be managed and analyzed via Atlas.ti.™

Collaboration and Interaction Plan

- The proposed interdisciplinary project brings together highly experienced investigators in diverse areas of research and clinical practices.
- The project is built from developing new collaborations between investigators across institutions including the University of Texas Health Science Center at Houston (UTHealth).
- The team will be led by

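### The caregiver interview script promises anonymity and no sharing outside the team, without exception, right after stating a legal duty to report suspected current mistreatment

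*Combined protocol and SAP*

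**What the plan says.** Appendix S holds the post-intervention interview guide. Its last part, on survivor treatment burden and caregiver stress, opens with a preamble addressed to the caregiver.

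The preamble states the interviewer's legal position: "However, I am obligated to inform you that Texas state law requires that I report suspicions of current mistreatment". The paragraph after that begins: "I want to reassure you that anything that you share with me today is completely anonymous". The same paragraph acknowledges that the interview is being recorded and says that "the data that you provide won't be shared outside of my research team". It ends with the handling of transcripts, "The transcripts that we produce will be de-identified", and an invitation to ask questions.

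Four numbered interview questions follow. The last concerns times when the caregiver felt overwhelmed.

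Two other places describe how the interview is handled. Appendix A (Description of Instruments) says that the principal investigator, a therapist or a research assistant conducts it after the intervention. The Data Management section covers recording and storage.

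**The concern.** The preamble sets the terms on which the caregiver decides what to say. It contains one specific statement that some content must leave the team, followed by two general statements, made without any qualification, that imply none will. A caregiver who takes the later sentences at face value may speak under a promise the study cannot keep. An interviewer who has just made that promise is also in an awkward position if a reportable matter comes up.

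What is at stake is participant protection and the accuracy of what people are told. The caregiver must live with the survivor (Inclusion Criteria), and most survivors will be enrolled because of mild to moderate cognitive impairment (Exclusion Criteria). The co-resident survivor is therefore the likely subject of any such report, although the script does not say whose mistreatment it means.

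**Working it through.** No arithmetic applies. The check sets each assurance beside the rest of the plan.

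**1. Is the interview anonymous?** Anonymity would mean that what is said cannot be linked to the speaker. Against that:
- The interviewer is a member of the study staff (Appendix A) and the interviewee is an enrolled member of a known dyad.
- The pre-intervention questionnaire (Appendix R) records the survivor's name, address, telephone number and email, and the caregiver's relationship to the survivor and date of birth.
- The Data Management section says: "Qualitative interview data will be digitally recorded; these raw audio files will be stored in a secure folder". A voice recording of an enrolled caregiver is not anonymous.
- De-identification is promised only for the transcribed material, in both Data Management and the script.

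What the plan delivers is confidentiality with de-identified transcripts. The anonymity statement is therefore untrue whether or not a report is ever made.

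**2. Can the no-sharing promise be kept?** In the ordinary case, yes: audio goes to a secure folder and de-identified transcripts go to the analysis software. When the reporting duty is triggered, no: a report required by state law passes information outside the research team. The promise as worded makes no allowance for this. Its conflict with the plan is conditional, unlike that in step 1.

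**3. Could the questions trigger the duty?** The probes under question 4 ask how far the caregiver was in control of their emotions, whether they behaved out of character, and how the survivor and the survivor's care were affected. One reads: "Tell me about a time when you might have pushed your loved one's buttons out of frustration". Two limits apply. The duty is worded for current mistreatment, whereas the probes ask for recollection of past occasions, so not every frank answer would be reportable. And question 4 comes last, so the assurance governs the whole list and does not immediately precede these probes. Even so, a recollection can give grounds to suspect something continuing, so the conditional conflict in step 2 could arise in practice.

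**4. How many people hear it?** The protocol plans 20 dyads with one caregiver each, so at most 20 caregivers. The documents give no rate of mistreatment or of disclosure, so the expected number of reports cannot be stated.

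**The case against.** The best defence is that the duty is stated first, openly, and is never taken back. On that reading the preamble gives a specific exception followed by a loosely worded general assurance, and the caregiver may ask about it. The no-sharing sentence also follows from the remark about recording and can be read as describing how the recorded data are handled, which matches Data Management. Much of this stands. A reader might infer that the script withdraws its own warning, or that both assurances are simply false. The text does not support either: the warning remains, and the no-sharing promise fails only when a report is due. What the defence does not rescue is the anonymity claim, which is wrong on any reading, or the lack of any link between the promise and its exception.

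A reader might also infer that the study has no route for handling a disclosure. That cannot be concluded. The script makes the interviewer the person who reports; the protocol separately says that all adverse events are documented and reported to the ethics committees, although it does not mention interview disclosures; and the public document is incomplete.

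Nor do the documents show that the credibility of the Specific Aim 3 findings is harmed. That aim concerns caregiver engagement in rehabilitation, whereas question 4 belongs to a separate block on burden and stress, and any effect on candour is conjecture.

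Finally, the consent form, which may describe the limits of confidentiality correctly, is not available here. Good consent wording would still be contradicted aloud by this script.

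**Conclusion.** The concern holds as a fault in what caregivers are told. The anonymity assurance is untrue under the plan's own interview and storage arrangements. The no-sharing assurance conflicts with the stated reporting duty whenever a report is required. This is wording that is wrong as written, so it is more than missing detail, and it should be corrected before further interviews.

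Its reach is every caregiver interviewed with this script, up to 20. It alters no estimate, test, endpoint or sample size. The conclusion assumes that the preamble is delivered as written and that a legally required report means disclosure outside the research team; it takes the legal duty as the script states it and does not depend on any further reading of Texas law.

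**What to change.** Replace the two assurances in the Appendix S preamble with wording the plan can honour, and restate the exception beside the promise. For example: *What you tell me is confidential, and the transcripts will have identifying details removed. The recording and your answers will stay within the research team, with the one exception I just mentioned: if I suspect that mistreatment is going on now, I have to report it.*

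Keep the existing sentence on the legal duty where it is, and check that the consent form says the same.

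The cost is about two sentences, plus whatever ethics review a script change requires. The downside is small: some caregivers may be slightly more guarded on question 4, although the reporting duty is already announced to them.
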